3.3.1. Management of Low Grade Chronic Toxicities

Since subjects will be receiving the study treatments daily, low grade chronic side effects, such as nausea, fatigue and diarrhea, while not meeting the above definition for dose limiting toxicities, may not be tolerable when experienced for long periods of time. Following discussion with the Gilead Sciences Medical Monitor, dose reduction may be permitted if low grade chronic side effects cannot be managed effectively with supportive care.

3.3.2. Specific Considerations for Managing Hyperbilirubinemia

3.3.2.1. Unconjugated (Indirect) Bilirubin Elevations

ENTO is an inhibitor of UGT1A1 and reversible increases in unconjugated (indirect) bilirubin values occurred in healthy subjects receiving ENTO. In the absence of symptoms or other hepatic laboratory abnormalities, ENTO dose modification is not required for elevated indirect bilirubin levels.

3.4. Duration of Treatment

For subjects enrolled to Group A Phase 1b (Dose Escalation):

ENTO lead-in will be administered daily on Days 1-14 as a single agent (Cycle 0) and will continue to be given daily in combination with IV daunorubicin (Days 1-3 for Cycle 1 and 2) and cytarabine (Days 1-7 for Cycle 1 and 2) during induction chemotherapy of every 14-day cycle for up to 2 cycles (Cycle 1 and 2). Subjects must be able to receive up to 2 cycles of induction chemotherapy. Cytarabine and daunorubicin (7+3) treatment (Cycle 1) may be started after 5 days of exposure to ENTO if the Principal Investigator agrees with the treating physician that treatment should start sooner. Subjects that experience a DLT may continue on protocol at a de-escalated dose.

Subjects with residual disease detected at the Cycle 1 Day 14 bone marrow evaluation will proceed with Cycle 2 of induction chemotherapy. The start of Cycle 2 will depend on the timing and result of the disease assessment. Subjects are to continue receiving ENTO while awaiting disease assessment results.

The investigator must consult the medical monitor if subjects have not obtained a CR after Cycle 1 and prior to Cycle 2, and if there is any consideration to omit Cycle 2 of induction chemotherapy.

If a subject discontinues study treatment (eg, as a result of an AE), every attempt should be made to keep the subject in the study to perform the required study-related follow-up and procedures. If this is not possible or acceptable to the subject or investigator, the subject may be withdrawn from the study.

For subjects enrolled to Group A Phase 2 (Dose Expansion):

ENTO 400 mg lead-in will be administered daily every 12 hours on Days 1-14 as a single agent (Cycle 0) to the completion of induction therapy as determined by bone marrow response. However, 7+3 treatment (Cycle 1) may be started earlier, after at least 5 days of exposure to ENTO, if the Principal Investigator agrees with the treating physician that treatment should start sooner.

ENTO 400 mg will be administered daily every 12 hours in combination with IV daunorubicin (Days 1-3) and cytarabine (Days 1-7) for up to 2 induction cycles (Cycle 1 and 2). Subjects must be able to receive 2 cycles of induction chemotherapy. Subjects with residual disease detected at the Cycle 1 Day 14 bone marrow evaluation proceed with Cycle 2 of induction chemotherapy. The start of Cycle 2 will depend on the timing and result of the disease assessment. Subjects are to continue receiving ENTO while awaiting disease assessment results.

The investigator must consult the medical monitor if subjects have not obtained a CR after Cycle 1 and prior to Cycle 2, and if there is any consideration to omit Cycle 2 of induction chemotherapy.

If CR/CRi is achieved at the end of Cycle 1 or 2, the subject may proceed to SCT or will receive post-remission chemotherapy. If CR/CRi is not achieved by the end of Cycle 2, the subject is considered a treatment failure and will have met study efficacy endpoint criteria, but will remain on study for required study-related follow-up procedures.

Post-remission chemotherapy will consist of $3\text{g}/\text{m}^2$ cytarabine every 12 hours on Days 1, 3, and 5 (< 60 years of age) or $1\text{g}/\text{m}^2$ high dose cytarabine once daily on Days 1-5 (\geq 60 years of age) in combination with ENTO every 12 hours on Days 1-28 of each 28-day cycle for at least 3 cycles and up to 4 cycles. Subjects who are awaiting a donor or transitioning to allogeneic SCT may receive at least 1 cycle and up to 4 cycles of cytarabine.

Maintenance therapy will consist of ENTO 400 mg as a single agent every 12 hours on Days 1-28 of each 28-day cycle and will continue for up to 12 cycles as long as the subject is experiencing benefit or until the subject becomes a candidate for SCT. Extension of maintenance may occur on an individual basis if approved by the Principal Investigator.

If a subject discontinues study treatment (eg, as a result of an AE), every attempt should be made to keep the subject in the study to perform the required study-related follow-up and procedures. If this is not possible or acceptable to the subject or investigator, the subject may be withdrawn from the study.

For subjects enrolled to Group B Phase 1b/2 (Dose Escalation and Expansion):

ENTO lead-in will be administered every 12 hours on Days 1-14 as a single agent (Cycle 0) for subjects enrolled to Group B Phase 1b and Group B Phase 2 safety run-in. However, chemotherapy with the assigned hypomethylating agent (Cycle 1) may be started earlier, after 5 days of exposure to ENTO, if the Principal Investigator agrees with the treating physician that treatment should start sooner.

For subjects enrolled to Group B Phase 2 randomization, ENTO lead-in will be administered every 12 hours on Days 1-5 as a single agent (Cycle 0).

In subsequent induction cycles (Cycles 1-4), ENTO will be administered every 12 hours on Days 1-28 in combination with assigned hypomethylating agent dose and schedule. Only azacitidine will be given during the Phase 2 safety run-in. Subjects will receive at least 2 cycles

of induction therapy but no more than 4 cycles. If the subject achieves < 5% blasts by morphology and flow cytometry or has evidence of clinical benefit after completing 2-4 induction cycles but is not eligible for SCT, the subject will have the option to receive maintenance therapy with ENTO in combination with decitabine or azacitidine. Subjects with persistent evidence of disease (ie, blasts \geq 5%) after Cycle 2 may receive up to 2 more induction cycles until subject achieves < 5% blasts. If < 5% blasts by morphology and flow cytometry is not achieved or the subject does not show evidence of clinical benefit after 4 induction cycles, the subject is considered a treatment failure and will be discontinued from the study.

During ENTO + hypomethylating agent maintenance therapy, ENTO will be administered every 12 hours on Days 1-28 in combination with assigned hypomethylating agent dose and schedule. ENTO will be administered every 12 hours on Days 1-28 in combination with decitabine on Days 1-5 or in combination with azacitidine on Days 1-7 of every 28-day cycle for at least 2 cycles. Subjects who are intolerant of the hypomethylating agent after completing 2 cycles may switch to ENTO monotherapy maintenance. Maintenance may continue as long as the subject is experiencing benefit and does not meet the criteria for study treatment discontinuation.

During ENTO maintenance therapy, ENTO will be administered as monotherapy every 12 hours on Days 1-28. Treatment may continue until the subject meets the criteria for study treatment discontinuation or up to 12 cycles. Extension of maintenance may occur on an individual basis if approved by the Principal Investigator.

If a subject discontinues study treatment (eg, as a result of an AE), every attempt should be made to keep the subject in the study to perform the required study-related follow-up and procedures. If this is not possible or acceptable to the subject or investigator, the subject may be withdrawn from the study.

For subjects enrolled to Group C Phase 1b (Dose Escalation):

ENTO monotherapy will be administered every 12 hours on Days 1-28 of every 28-day cycle until the subject meets the criteria for study treatment discontinuation (see Section 6.4.1). Subjects who experience a DLT may continue on protocol at a de-escalated dose.

If a subject discontinues study treatment (eg, as a result of an AE), every attempt should be made to keep the subject in the study to perform the required study-related follow-up and procedures. If this is not possible or acceptable to the subject or investigator, the subject may be withdrawn from the study.

For subjects enrolled to Group C Phase 2 (Dose Expansion):

ENTO monotherapy will be administered every 12 hours on Days 1-28 of every 28-day cycle and may continue as long as the subject is experiencing benefit and does not meet criteria for study treatment discontinuation.

If a subject discontinues study treatment (eg, as a result of an AE), every attempt should be made to keep the subject in the study to perform the required study-related follow-up and procedures. If this is not possible or acceptable to the subject or investigator, the subject may be withdrawn from the study.

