ENTO will be administered orally every 12 hours as a monotherapy lead-in on Days 1-14 (Cycle 0), and will be administered orally every 12 hours on Days 1-28 in combination with decitabine on Days 1-10 of every 28-day cycle for at least 2 but no more than 4 cycles of induction chemotherapy. Subject will undergo a bone marrow aspiration and biopsy on Cycle 2 Day 28. Subjects who have a CR/CRi can proceed to SCT per investigator's discretion or to maintenance therapy with ENTO + decitabine. Subjects with persistent AML will receive 2 more cycles of induction chemotherapy and a bone marrow aspiration and biopsy will be performed at Cycle 4 Day 28. Subjects who have persistent leukemia at this time point will be considered a treatment failure and come off study. Subjects ineligible for SCT will have the option to receive maintenance therapy with ENTO + decitabine. Subjects who are intolerant of decitabine after completing 2 cycles will switch to ENTO monotherapy maintenance. Maintenance will continue as long as the subject experiences benefit and does not meet criteria for study treatment discontinuation. Extension of maintenance may occur on an individual basis if approved by the Principal Investigator.

Group B Phase 2 (Dose Expansion)

Note: At the time of this amendment, Group B Phase 2 safety run-in had completed enrollment. In Phase 2, the overall safety of ENTO in combination with a hypomethylating agent (decitabine or azacitidine)

will be evaluated. As part of the safety run-in, ENTO in combination with azacitidine will be administered to 6 evaluable subjects. Following completion of the safety run-in (DLT window, Section 3.2), the azacitidine arm will be evaluated to determine if enrollment of the expansion cohort may proceed with azacitidine. If 2 or more subjects experience DLTs, all ongoing subjects in the safety run-in will be discontinued, the azacitidine arm will be dropped from the study, and subjects in the expansion phase will only receive ENTO in combination with decitabine.

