Hydroxyurea is allowed during the lead-in period per investigator discretion and after discussion with the medical monitor. Hydroxyurea should be discontinued prior to initiating hypomethylating agent.

If circulating blasts have cleared at the end of monotherapy lead-in (Cycle 0 Day 5), then a bone marrow aspirate will be performed for disease assessment.

Subjects with cytogenetic and molecular mutations at screening must have cytogenetic and molecular mutation testing repeated at subsequent bone marrow examinations (Cycle 0 Day 5, Cycle 1 Day 28, count recovery, End of Study).

Entospletinib + Hypomethylating agent induction (Cycles 1-4): In subsequent induction cycles (Cycles 1-4), ENTO 400 mg will be administered orally every 12 hours on Days 1-28 in combination with the assigned hypomethylating agent dose and schedule. All subjects will receive at least 2 but no more than 4 cycles of induction chemotherapy.

Table 3-3. Hypomethylating Agent Dose and Schedule Table (Induction)

Agent	Dose	Days	Cycle Duration
decitabine	20mg/m ²	1-10	28 days
azacitidine	75mg/m ²	1-7	

A bone marrow aspirate and biopsy sample will be collected for disease assessment and biomarker research at the end of every 2 cycles (Cycle 2 Day 28 and Cycle 4 Day 28) or as clinically indicated. Subjects with cytogenetic and molecular mutations at screening must have cytogenetic and molecular mutation testing repeated at subsequent bone marrow examinations (Cycle 0 Day 14, Cycle 1 Day 28, count recovery, End of Study).

If the subject achieves < 5% blasts by morphology and flow cytometry or has evidence of clinical benefit after completing 2-4 induction cycles but is not eligible for SCT, the subject will have the option to receive maintenance therapy with ENTO in combination with decitabine or azacitidine. Subjects with persistent evidence of disease (ie, blasts ≥ 5%) after Cycle 2 may receive up to 2 more induction cycles until subject achieves < 5% blasts.

If < 5% blasts by morphology and flow cytometry is not achieved or the subject does not show evidence of clinical benefit after 4 induction cycles, the subject is considered a treatment failure and will have met study efficacy endpoint criteria, but will remain on study for required study-related follow-up procedures.

Entospletinib + Hypomethylating agent maintenance (at least 2 cycles): ENTO will be administered orally every 12 hours on Days 1-28 in combination with assigned hypomethylating agent dose and schedule.

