6.4.1. Criteria for Discontinuation of Study Treatment

Study treatment may be discontinued in the following instances:

- Intercurrent illness that would, in the judgment of the investigator, affect assessments of clinical status to a significant degree. Following resolution of intercurrent illness, the subject may resume study dosing at the discretion of the investigator.
- Unacceptable toxicity, or toxicity that, in the judgment of the investigator, compromises the ability to continue study-specific procedures or is considered to not be in the subject's best interest
- Group C subjects with the following increases in pre-treatment baseline blast percentage in the bone marrow:
 - < 5% blasts at baseline with an increase to $\geq 10\%$ blasts
 - 5 to 10% blasts at baseline with an increase to $\geq 20\%$ blasts
 - 11 to 20% blasts at baseline with an increase to $\geq 30\%$ blasts
 - **Exception:** Subjects will be allowed to continue therapy for up to 2 cycles. If at the time of the post Cycle 2 disease assessment there has not been an improvement in cytopenias or blast count, peripheral blood or marrow, that would suggest clinical benefit, the subject is to be removed from study. Decisions regarding continuation of therapy in subjects on Group C past Cycle 2 will be reviewed with the PI and Medical Monitor.
- Subjects may be removed in the case of new CNS disease or other new sites of extramedullary involvement
- Groups B and C: requires continued treatment with hydroxyurea after Cycle 1

- Subject request to discontinue for any reason. Subjects who withdraw from the study treatment phase of the study should still be followed for survival until 3 years from study start (see Section 6.5, Long term follow up)
- Subject noncompliance with study treatment administration, study procedures, or study requirements should be withdrawn from study treatment in circumstances that increase risk or substantially compromise the interpretation of study results
- Pregnancy during the study (refer to Appendix 4)
- The investigator, in consultation with the Gilead Sciences Medical Monitor or designee, may withdraw any subject from the study treatment, if, in the investigator's opinion, it is not in the subject's best interest to continue.
- Discontinuation of the study at the request of Gilead, a regulatory agency or an institutional review board or independent ethics committee (IRB/IEC)

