6.4.2. End of Study Treatment

Subjects will be removed from study treatment when any of the criteria listed in Section 6.4.1 apply. The following procedures will be conducted when a subject discontinues study treatment and prior to initiating a new therapy.

- Review prior/concomitant medication
- Record any adverse events
- ECOG performance status
- Physical exam
- Vital signs; including blood pressure, respiratory rate, pulse, temperature, oxygen saturation level
- Weight
- Obtain blood samples for:
 - Chemistry
 - Hematology
 - Coagulation

- Biomarker testing
- **Phase 1b only:** For Group C subjects dosed with 400 mg and 800mg ENTO, a BAT assay sample may be collected
- Obtain bone marrow aspirate and biopsy samples for disease assessment and biomarker testing (if not performed within the last 2 weeks). If the bone marrow is consistent with Morphologic CR or CRi status per [Appendix 5](#), then evaluate MRD as per institutional practice and [Appendix 7](#).
- **CCI** [REDACTED]

6.4.3. 30-day Follow-up

After the last dose of study drug, subjects should be followed for any drug-related AEs and/or ongoing serious adverse events (SAEs) until those events have resolved or become stable, whichever occurs later. The site will contact the study subject regardless of AE/SAE status approximately 30 days after the subject's last dose of study drug to assess adverse events since the last study visit and review concomitant medications. Contact the subject by phone (or in person, if necessary) to assess the subject's condition and record any adverse events reported during the follow-up contact. Document the phone call or visit.

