6.5. Long Term Follow-up

Long term follow-up for survival will be conducted every 6 months (\pm 4 weeks) after the End of Study Treatment visit for up to 3 years (since the start of study therapy). Information to be gathered includes leukemia treatments, other malignancies, and survival. This follow-up can be done during a routine clinic visit, other contact with the subject, or via telephone. Gilead reserves the right to discontinue or shorten the duration of participation in the long term follow-up period at any time. See section [9.3.4](#) for details regarding study discontinuation.

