8.5.2. Time-to-Event Endpoints

For a subject who is not known to have relapsed or died by the end of the study follow-up or data cutoff, RFS is censored on the date of the last available assessment of the subject.

For subjects with none of the events defined in EFS before the end of the study follow-up or data cutoff, EFS is censored at the date of the last available assessment of the subject.

For a subject who is not known to have died by the end of study follow-up or data cutoff, OS is censored on the date the subject was last known to be alive.

RFS, EFS and OS will be analyzed using Kaplan-Meier (KM) methods. The KM estimate of the survival function will be computed and the results will be presented using KM curves. The median will be provided along with the corresponding 95% CI. Additionally, the 25% and 75% percentiles for these endpoints will also be provided.

For subjects who die without report of relapse, remission duration is censored on the date of death, regardless of cause. For a subject with no report of relapse by the end of the study follow-up or data cutoff date, observation is censored on the date of the last available assessment of the subject.

Analysis of remission duration will be analyzed using cumulative incidence by considering competing risks. The estimate of the cumulative incidence of relapse (CIR) will be reported with the associated 95% CI.

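### Protocol Section 3.4 takes Group B treatment failures off the study while Sections 3.1.3, 3.1.4 and 6.3.2 keep them on; where a site follows 3.4, overall survival is informatively censored soon after failure.

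*Protocol*

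**What the plan says.** **Texts that take Group B failures off study**

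- Protocol 3.4, in the part headed Group B Phase 1b/2: after four induction cycles without response, "the subject is considered a treatment failure and will be discontinued from the study".
- Protocol Synopsis, Group B Phase 1b, on the Cycle 4 Day 28 marrow: "Subjects who have persistent leukemia at this time point will be considered a treatment failure and come off study". SAP 1.2 repeats this, also under Group B Phase 1b.

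**Texts that keep the same subjects on study**

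- Protocol 3.1.3 (Phase 1b), 3.1.4 (Phase 2) and 6.3.2 (procedures): the failing subject counts as having reached the efficacy endpoint, "but will remain on study for required study-related follow-up procedures".

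**Texts on survival**

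- Protocol 6.5: "Long term follow-up for survival will be conducted every 6 months" after the End of Study Treatment visit, up to 3 years from the start of therapy. The sponsor may shorten this.
- Protocol 6.4.1, in the bullet on discontinuation at the subject's request: such subjects "should still be followed for survival until 3 years from study start".
- Protocol 8.5.2 and SAP 6.2.2: for a subject not known to have died, "OS is censored on the date the subject was last known to be alive".

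**The concern.** The two instructions cannot both be followed. A subject discontinued from the study has no further scheduled contact; a subject who remains on study has survival contact every six months.

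The choice matters because OS is a secondary endpoint. Subjects who fail induction are plausibly those with the shortest remaining survival. Censoring them when they fail breaks the independence between censoring and prognosis that Kaplan-Meier needs, and beyond about month 4 or 5 the curve would describe mainly responders. If some sites follow Section 3.4 and others Section 3.1.4, completeness of follow-up also differs by site.

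**Working it through.** **1. Is the Section 3.4 wording just loose language for stopping treatment?** Section 3.4 itself suggests not.

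- It says that Group A Phase 2 failures remain on study, then says the opposite for Group B. A site could take that as deliberate.
- The closing paragraph of its Group B part distinguishes stopping study treatment from being withdrawn from the study. The failure sentence uses the second term.

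**2. Does another section settle it?** Section 6.5 schedules survival contact but does not address subjects already discontinued from the study. The survival clause in 6.4.1 sits in the bullet on subject request and does not mention failures. No section states precedence.

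**3. When would a failure be censored?** The lead-in is 5 days (randomized part) or 14 days (Phase 1b and safety run-in), followed by at most 4 × 28 = 112 days of induction. SAP 6.2.2 uses 30.4375 days per month.

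- Randomized: 5 + 112 = 117 days; 117 / 30.4375 = 3.84 months.
- 14-day lead-in: 14 + 112 = 126 days; 126 / 30.4375 = 4.14 months.
- Adding the 30-day contact of Protocol 6.4.3: 147 and 156 days, or 4.83 and 5.13 months.

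Of 36 planned months, 36 − 5.13 = 30.9 to 36 − 3.84 = 32.2 months of survival information could be lost per surviving failure.

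**4. How large could the bias be?** The plan states no OS assumption, so there is no plan figure to reproduce. The following are my assumptions:

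- Survival is exponential, with median mR = 12 or 15 months in responders and mF = 6 or 8 months in failures.
- The failure share is q = 40%, 50% or 60%. This brackets the 50% composite remission rate assumed for Group B in Protocol 8.9.
- Every failure still alive at exit time t0 is lost. This is a worst case.

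With full follow-up, S(t) = (1 − q)·0.5^(t/mR) + q·0.5^(t/mF). If failures are censored at t0, the large-sample Kaplan-Meier curve follows S(t) up to t0 and then falls at the responder rate. Its median is t0 + mR·log2(S(t0)/0.5), provided S(t0) exceeds 0.5, which holds throughout.

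Worked case, q = 0.5, mR = 15, mF = 6, t0 = 3.84:

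- S(3.84) = 0.5 × 0.837 + 0.5 × 0.641 = 0.739.
- Censored median = 3.84 + 15 × log2(0.739/0.5) = 12.3 months.
- Full follow-up median, solving S(t) = 0.5, is 9.2 months. The overstatement is 3.1 months.

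Over all 12 combinations, the smallest effect is at q = 40% with medians 12/8, and the largest at q = 60% with medians 15/6:

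| Exit t0 (months) | Smallest: full to censored median | Largest: full to censored median | Overstatement (months) |
|---|---|---|---|
| 3.84 | 10.15 to 11.26 | 8.37 to 11.73 | 1.1 to 3.4 |
| 4.5 | 10.15 to 11.13 | 8.37 to 11.21 | 1.0 to 2.8 |
| 5.13 | 10.15 to 11.02 | 8.37 to 10.72 | 0.9 to 2.4 |

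The 4.5-month row lies between the exit times with and without the 30-day contact. The share of all subjects censored at exit is q·0.5^(t0/mF). At 3.84 months this runs from 0.4 × 0.5^(3.84/6) = 26% to 0.6 × 0.5^(3.84/8) = 43%.

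**5. Is EFS affected?** Treatment failure is itself an EFS event, so later loss of contact changes little. The exception is a partial remission: SAP 6.2.2 does not count it as treatment failure, but with 5% or more blasts it can be a failure under Section 3.4.

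**The case against.** The best counter-argument is that the documents as a whole intend survival follow-up to continue.

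- The Group B part of Section 3.4 asks for every attempt to keep subjects in the study after treatment stops, and Section 6.4 repeats it.
- Both Group B procedure tables in Appendix 2 carry a 3-year survival column with no exemption for failures.
- Section 7.3 asks for deaths after the post-treatment visit to be reported.
- The protocol is elsewhere loose about the word study: Section 6.4.1 speaks of removal from study within a list of reasons to stop treatment.

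This stands as evidence of intent, and it makes alignment with follow-up the safe choice. It does not cancel the explicit contrary sentence.

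Three stronger readings are tempting but unsupported:

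- A reader might infer that the plan as a whole censors OS at failure. It does not. The bias arises only where a site follows Section 3.4, and the last-known-alive rule can move the censoring date to the 30-day contact ("The site will contact the study subject regardless of AE/SAE status approximately 30 days after" the last dose).
- A reader might infer that the Synopsis and SAP 1.2 take all Group B failures off study. Their sentence covers Phase 1b only; for the randomized part, Section 3.4 is the only conflicting text.
- A reader might take the figures above as an estimate of actual bias. They assume that every surviving failure is lost at every site. Section 3.4 also applies only to failure after four cycles, and the SAP says that the study ends early, so 36 months of follow-up may not be reached for anyone.

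OS is also descriptive, with about 20 subjects per arm planned and no formal comparison.

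**Conclusion.** The contradiction is certain and unresolved: Section 3.4 is incompatible with 3.1.3, 3.1.4 and 6.3.2, and one side is wrong as written. The effect on OS is conditional. Where Section 3.4 is followed, failures are censored at about 3.8 to 4.1 months, or up to about 5 months with the 30-day contact. The bias is upward if failures die sooner than responders, and nil if they do not.

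Under the assumed medians and failure shares, the worst-case overstatement of median OS is about 1.0 to 2.8 months (exit at 4.5 months) or 1.1 to 3.4 months (exit at 3.84 months). Confidence is high in the contradiction and low in any particular size. The point should be corrected, but it does not undermine the response endpoints and leaves EFS largely intact.

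**What to change.** - Reconcile Protocol 3.4, the Synopsis and SAP 1.2 with Protocol 3.1.3, 3.1.4, 6.3.2 and 6.5, so that stopping study treatment is distinct from leaving the study.
- State that Group B treatment failures stay in the Section 6.5 survival follow-up, up to 3 years or until the sponsor ends follow-up, unless consent is withdrawn.
- While editing, reconcile when failure is declared: Section 6.3.2 refers to 2 to 4 induction cycles, whereas 3.1.3, 3.1.4 and 3.4 refer to 4.
- Add to the SAP a listing of Group B failures with no survival contact after the failure date, so that any effect on reported OS is visible.

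The cost is a few sentences and one listing. Section 6.5 already plans the contacts, so no visits or subjects are added. SAP Section 1 says that the SAP is finalized before the database, so the listing is useful even though Group B recruitment has closed.
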